7.1.2 SECONDARY ENDPOINTS

This study has a number of secondary efficacy endpoints:

7.1.2.1 TIME TO FIRST TREATMENT ESCALATION

For patients who experience a treatment step-up (as defined in section 7.1.1), the Treatment Escalation Status and Time to First Treatment Escalation will be recorded as follows:

- Status = 1
- Time = Date of first treatment escalation – Date of initiation on tofacitinib

For patients who don't experience a treatment escalation, the Treatment Escalation Status and time to first treatment escalation will be recorded as follows:

- Status = 0

-
- Time = Date of final visit – Date of initiation on tofacitinib

If a patient is lost to follow-up or withdraws from the study, they will be censored at the date of their last visit.

The analysis for time to first treatment escalation type step-up may be extended to escalation type step-down.

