7 ENDPOINTS AND COVARIATES

7.1 EFFICACY/ EFFECTIVENESS ENDPOINT(S)

7.1.1 PRIMARY ENDPOINTS

Number and timing of treatment escalations of tofacitinib patients in 24 months, where Treatment Escalation in this study is defined as a switch to another DMARD or combination of DMARDs when compared to the last visit.

The following types of escalations will be distinguished:

1. Treatment **Termination**, which is the termination of a DMARD (or multiple when on combination therapy) without starting a new DMARD therapy. Premature study terminations (without documented treatment termination) will not be considered treatment terminations.
2. Treatment **Step-up** which is an increase from the current treatment regime towards e.g. a combination of DMARDs
3. Treatment **Step-down**, which is a de-escalation from the current treatment regime, e.g. from combination therapy to monotherapy

Patients start their therapy at baseline with tofacitinib either in Monotherapy or in Combination therapy with MTX. Subsequent therapy changes are documented on eCRF instrument “Rheumatologische Medikation“ by:

- adding additional DMARDs on top of the current therapy
- stopping the current DMARD in monotherapy and adding a new DMARD
- stopping one of multiple DMARDs when on combination therapy
- stopping one of multiple DMARDs when on combination therapy and adding a new DMARD
- stopping all DMARDs and not starting a new therapy. The escalation types depend on the combination of DMARD classes (tsDMARD vs bDMARD vs TNFi vs csDMARD). The eCRF does not explicitly distinguish between tsDMARD vs bDMARD vs TNFi, but combines all rheumatic medications belonging to the above classes under

tsDMARD/bDMARD. For the definition of treatment escalations, the following assignment of rheumatic medication to DMARD classes will be done:

tsDMARDs:

- baricitinib
- upadacitinib
- filgotinib

TNFi:

- etanercept
- adalimumab
- certolizumab
- golimumab
- infliximab

bDMARDs (excluding TNFi):

- abatacept
- rituximab
- anakinra
- tocilizumab
- sarilumab

For details of treatment escalations, e.g., which DMARD class addition or reduction leads to a particular escalation type, see table 12.2 in section 12.1.2.

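### SAP 7.1.2.1 defines the time-to-first-escalation event by step-up but words its date and its censored group by escalation of any type, so literal programming can misdate events and leave some patients without a status

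*SAP*

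**What the plan says.** SAP 7.1.1 defines the umbrella term: "Treatment Escalation in this study is defined as a switch to another DMARD or combination of DMARDs when compared to the last visit". It continues with "The following types of escalations will be distinguished" and lists termination, step-up and step-down. It describes a step-down as a change "which is a de-escalation from the current treatment regime, e.g. from combination therapy to monotherapy". In this SAP a de-escalation is therefore a type of escalation.

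SAP 7.1.2.1 sets up secondary endpoint a) in three lines:

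- Status = 1: "For patients who experience a treatment step-up (as defined in section 7.1.1), the Treatment Escalation Status and Time to First Treatment Escalation will be recorded".
- Event time: "Time = Date of first treatment escalation – Date of initiation on tofacitinib".
- Status = 0: "For patients who don't experience a treatment escalation, the Treatment Escalation Status and time to first treatment escalation will be recorded as follows", with time running to the final visit.

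The section closes by calling this the analysis for escalation of type step-up and allows an extension to step-down. SAP 8.1, whose heading names this endpoint, sets the time at the occurrence of the event of interest. It gives status 0 at the last visit to patients without that event. Protocol 6.1.2 a) lists time to first treatment escalation with no restriction to step-up.

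**The concern.** The rule uses a narrow term to decide who has an event, and a wider term to decide when it happened and who is censored. Two patient courses show the effect.

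1. A patient on tofacitinib plus MTX drops MTX at month 3 (a step-down) and moves to a TNF inhibitor at month 15 (a step-up). The patient qualifies for Status = 1. The first escalation, in the sense of 7.1.1, is at month 3, so the event is dated 12 months before the step-up.
2. A patient whose only change is dropping MTX, or stopping without a new drug, has had an escalation but no step-up. Neither the Status = 1 line nor the Status = 0 line of 7.1.2.1 applies.

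At stake is whether the Kaplan-Meier curve for this endpoint describes step-ups, a mixture of step-up and other dates, or any change of treatment.

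**Working it through.** **Figures in the plan.** The documents give no event rate, count or power for this endpoint. The sizing in Protocol 7.7 concerns the recurrent-event primary analysis. There is nothing to reproduce, so the check traces patients through the text and then illustrates the size under assumed rates.

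**Patients traced through the rules**

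| Course | 7.1.2.1 read with the 7.1.1 definition | 8.1 with step-up as the event |
|---|---|---|
| Step-up is the first change | Status 1, dated at step-up | Same |
| Step-down or termination, then step-up | Status 1, dated at the earlier change | Status 1, dated at step-up |
| Step-down only or termination only | Neither line applies | Status 0 at last visit |
| No change | Status 0 at final visit | Same |

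The two sources disagree in the second and third rows.

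**Illustration (all rates assumed).** Constant, independent hazards; 24 months of complete follow-up; counts scaled to the planned 1500 patients. Let u be the step-up hazard and o the combined step-down and termination hazard, both per 24 months.

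- Free of step-up at 24 months: exp(−u)
- No status in 7.1.2.1: N = exp(−u)·[1 − exp(−o)]
- Step-ups preceded by another type: M = [1 − exp(−u)] − u/(u+o)·[1 − exp(−(u+o))]
- 24-month estimate if patients without a status are dropped: exp(−(u+o))/(1 − N)
- 12-month estimate with correct dates: exp(−u/2)
- 12-month estimate with any-type dates and 8.1 censoring: 1 − {[1 − exp(−u/2)] + [exp(−u/2) − exp(−u)]·[1 − exp(−o/2)]}

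Worked for u = 0.5, o = 0.5 (step-down 0.3, termination 0.2):

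- exp(−0.5) = 0.607
- N = 0.607 × 0.393 = 0.239, or 358 of 1500
- M = 0.393 − 0.5 × 0.632 = 0.077, or 116 of 1500
- If dropped: 0.368/0.761 = 0.48
- 12 months, correct dates: exp(−0.25) = 0.779
- 12 months, any-type dates: 1 − (0.221 + 0.172 × 0.221) = 0.741

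| Step-up / step-down / termination | No status per 1500 | Misdated per 1500 | 12 months: correct vs any-type dates with 8.1 | 24 months: 8.1 supplies Status 0 | 24 months: dropped |
|---|---|---|---|---|---|
| 0.5 / 0.1 / 0.1 | 165 | 51 | 0.78 vs 0.76 | 0.61 | 0.56 |
| 0.5 / 0.3 / 0.2 | 358 | 116 | 0.78 vs 0.74 | 0.61 | 0.48 |
| 0.5 / 0.6 / 0.3 | 540 | 187 | 0.78 vs 0.72 | 0.61 | 0.39 |
| 1.0 / 0.6 / 0.3 | 327 | 277 | 0.61 vs 0.52 | 0.37 | 0.19 |

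The 12- and 24-month columns are proportions free of step-up. A simulation of 150,000 patients under the same assumptions agrees to within 3 patients per 1500 and puts the misdated events 7.7 to 8.1 months too early on average.

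The 24-month value is the same whether events carry the correct or the any-type date, because everyone with a step-up by month 24 counts as an event under both. Counting any type as the event, as Protocol 6.1.2 a) can be read, gives exp(−(u+o)): 0.50, 0.37, 0.25 and 0.15 in the four rows.

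**The case against.** The best defence is that the intended event is clear. The last sentence of 7.1.2.1 labels the analysis as type step-up, so the first escalation in the time line can be read as the first of that type. SAP 8.1 then fills the gap: patients without the event of interest are censored at the last visit, and events are dated when they occur. SAP 6.6 points the same way by placing step-down patients in the group without a switch up.

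Most of this stands. It makes first step-up the likely intention and removes any certainty that the curve will be wrong. A reader might infer that the plan removes step-down-only and termination-only patients from the risk set, so that step-ups will appear more frequent than they were. The documents do not support that, because no section says to drop anyone and 8.1 provides a censoring rule.

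The defence does not remove the contradiction. SAP 8.1 never names the event of interest, and its heading also covers the primary analysis, in which all three types count. SAP 6.6 does not mention terminations in that subgroup. The time and Status = 0 lines of 7.1.2.1 still use the wider term, and a programmer would normally apply the endpoint-specific rule first. By contrast, the drug survival rule in SAP 7.1.2.10 uses one term, termination, for the event, the date and the censored group.

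**Conclusion.** The concern holds as an internal inconsistency in the definition of a secondary endpoint. Read literally with 7.1.1, section 7.1.2.1 can date a step-up at an earlier step-down or termination and assigns no status to patients with only those changes. An incorrect curve is a risk of literal programming and not an established result.

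The size is unknown. Under the assumed hazards:

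- If 8.1 supplies Status = 0, the 24-month estimate is unchanged and the curve is too low before then, by 0.02 to 0.09 at 12 months.
- Only if patients without a status are dropped does the 24-month proportion free of step-up fall, from 0.61 to between 0.56 and 0.39, or from 0.37 to 0.19.

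These figures rest on constant, independent hazards and no dropout, none of which comes from the documents.

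Two related matters remain open. Restricting the event to step-up narrows the protocol endpoint without saying so. The analysis set also conflicts: SAP 9.2.3.1 names the SFAS, which holds on-tofacitinib data only, while the table in 9.2.6 names the FAS. For patients who stop tofacitinib, that conflict leaves the censoring date unsettled.

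**What to change.** Reword SAP 7.1.2.1 along these lines:

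- Patients with a step-up: Status = 1, Time = date of first step-up minus date of tofacitinib initiation.
- All other patients, including those with only step-downs or terminations: Status = 0, censored at the last visit as in 8.1.
- If the optional step-down curve is produced, use the same pattern with the date of first step-down.

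Record the step-up restriction as a narrowing of Protocol 6.1.2 a), or also report time to first escalation of any type. Reconcile SFAS in 9.2.3.1 with FAS in 9.2.6, and state the resulting censoring date for patients who stop tofacitinib.

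The cost is a few sentences of SAP text and the matching table entry. No new data are needed; the optional any-type analysis would add one output.

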7.1.2.2 RATE OF LDA

The Rate of Low Disease Activity (LDA) will be calculated over time for patients taking tofacitinib using 4 different definitions:

- a) SDAI ≤ 11 ;
- b) CDAI ≤ 10 ;
- c) DAS 28-4 (ESR) ≤ 3.2 and
- d) DAS 28-4 (CRP) ≤ 3.2 .

These are defined in detail below.

7.1.2.2.1 SDAI LDA

At each time point (M3, M6, M9, M12, M15, M18, M21, M24) SDAI LDA is derived as:

$$\begin{aligned} \text{SDAI_LDA} &= 1 \text{ if} & \text{SDAI} &\leq 11 \\ \text{SDAI_LDA} &= 0, & \text{otherwise.} \end{aligned}$$

The proportion of patients in SDAI LDA at Month X is then calculated as:

No. of patients with SDAI LDA at Month X / Total Number of patients with non-missing SDAI LDA at Month X.

7.1.2.2.2 CDAI LDA

At each time point (M3, M6, M9, M12, M15, M18, M21, M24) CDAI LDA is derived as:

$$\begin{aligned} \text{CDAI_LDA} &= 1 \text{ if} & \text{CDAI} &\leq 10 \\ \text{CDAI_LDA} &= 0, & \text{otherwise.} \end{aligned}$$

The proportion of patients in CDAI LDA at Month X is then calculated as:

No. of patients with CDAI LDA at Month X / Total Number of patients with non-missing CDAI LDA at Month X.

7.1.2.2.3 DAS28-4 (ESR) LDA

At each time point (M3, M6, M9, M12, M15, M18, M21, M24) DAS 28-4 (ESR) LDA is derived as:

$$\begin{aligned} \text{DAS 28-4 (ESR) LDA} &= 1 \text{ if } \text{DAS 28-4 (ESR)} \leq 3.2. \\ \text{DAS 28-4 (ESR) LDA} &= 0, \quad \text{otherwise.} \end{aligned}$$

DAS28-4 (ESR) is calculated as in Section 7.1.2.4.1

The proportion of patients in DAS 28-4 (ESR) LDA at Month X is then calculated as:

No. of patients with DAS 28-4 (ESR) LDA at Month X / Total Number of patients with non-missing DAS 28-4 (ESR) LDA at Month X.

7.1.2.2.4 DAS28-4 (CRP) LDA

At each time point (M3, M6, M9, M12, M15, M18, M21, M24) DAS 28-4 (CRP) LDA is derived as:

$$\begin{aligned} \text{DAS 28-4 (CRP)}_{\text{LDA}} &= 1 \text{ if } \text{DAS28-4 (CRP)} \leq 3.2. \\ \text{DAS 28-4 (CRP)}_{\text{LDA}} &= 0, \quad \text{otherwise.} \end{aligned}$$

DAS28-4 (CRP) is calculated as in Section 7.1.2.4.1

The proportion of patients in DAS 28-4 (CRP) LDA at Month X is then calculated as:

No. of patients with DAS 28-4 (CRP) LDA at Month X / Total Number of patients with non-missing DAS 28-4 (CRP) LDA at Month X.

7.1.2.3 RATE OF REMISSION

The Rate of Remission will be calculated over time for patients taking tofacitinib, using 5 definitions:

- a) American College of Rheumatology (ACR) – European League Against Rheumatism (EULAR) Boolean remission criteria;
- b) Simplified Disease Activity Index (SDAI) ≤ 3.3 ;
- c) Clinical Disease Activity Index (CDAI) ≤ 2.8 ;
- d) DAS 28-4 (ESR) < 2.6 and
- e) DAS28-4 (CRP) < 2.6

These are defined in more detail below.

7.1.2.3.1 ACR-EULAR BOOLEAN REMISSION CRITERIA

At each time point (M3, M6, M9, M12, M15, M18, M21, M24) ACR Remission is derived as:

$ACR_Remission = 1$, if: $SJC28 \leq 1$, $TJC28 \leq 1$, $CRP \leq 1$ mg/dL, and $PtGA \leq 2$ cm

$ACR_Remission = 0$, Otherwise.

The proportion of patients in ACR Remission at Month X is then calculated as:

No. of patients with ACR Remission at Month X / Total Number of patients with non-missing ACR Remission at Month X.

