7.6.7. Effectiveness criteria

The effectiveness of the treatment with Tofacitinib will be documented using the following tools for the evaluation of the course of the disease:

Table 8. Disease Activity Indicators

Indicator	Definition/Calculation
DAS28-4 (CRP)	$0.56*\sqrt{(TJC28)} + 0.28*\sqrt{(SJC28)} + 0.36*\ln(CRP \text{ in mg/l} + 1) + 0.014*PtGA \text{ in mm} + 0.96$
DAS28-4 (ESR)	$0.56*\sqrt{(TJC28)} + 0.28*\sqrt{(SJC28)} + 0.70*\ln(ESR \text{ in mm/hour}) + 0.014*PtGA \text{ in mm}$
Simplified Disease Activity Index (SDAI)	$(TJC28) + (SJC28) + [\text{PhyGA in cm}] + [\text{PtGA in cm}] + [\text{CRP in mg/dL}]$
Clinical Disease Activity Index (CDAI)	$(TJC28) + (SJC28) + [\text{PhyGA in cm}] + [\text{PtGA in cm}]$
ACR/EULAR Boolean-based definition of remission	A patient must satisfy all of the following: tender joint count ≤ 1 , swollen joint count ≤ 1 , CRP $\leq 1 \text{ mg/dL}$, subject's global assessment of arthritis ≤ 1 on a 0-10 scale

TJC = tender joint count; SJC = swollen joint count; CRP = C-reactive protein in mg/L; ESR = erythrocyte sedimentation rate in mm/first hour, PtGA = Patient's Global Assessment of Arthritis; PhyGA = Physician's Global Assessment of Arthritis

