7.6.10. Patient Global Assessment of Arthritis (PtGA)

Patients will answer the following question, “Considering all the ways your arthritis affects you, how are you feeling today?” The patient’s response will be recorded using a 100 mm VAS with anchors on 0 = very well and 100 = very poorly.

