7.9. Data analysis

This section gives an overview of the key methods and derivations required for the study. Detailed methodology for summary and statistical analyses of data collected in this study will be documented in a Statistical Analysis Plan (SAP), which will be dated, filed and maintained by the sponsor. The SAP may modify the plans outlined in the protocol; any major modifications of primary endpoint definitions or their analyses would be reflected in a protocol amendment. SAS (Version 9.1, 9.2, 9.3 or 9.4) will be used for all analyses.

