10. PLANS FOR DISSEMINATING AND COMMUNICATING STUDY RESULTS

10.1. Communication of study results

It is planned that there will be at least one interim analysis. Results of interim analyses as described in the SAP are planned to be presented on national and international congresses. Final study results are additionally planned to be published peer-reviewed journals.

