2 AMENDMENTS FROM PREVIOUS VERSION(S)

The Protocol A3921302_ObservationalPlan_Finalv1.1_23Aug2017.docx states that:

In order to collect comparable study data, visits 2 to 9 occurring +/- 14 days of the scheduled visit date will be used for data analysis.

As the visits will be scheduled according to clinical practice there are likely to be many visits outside of the windows defined in the protocol. To ensure the primary analysis incorporates all visits at which a patient might experience a treatment escalation all visits will be included. A further per-protocol analysis will be conducted using the analysis windows set out in Section 12.1.1.

Populations used during interim analyses were updated.

Additional details regarding the definition of the primary endpoint were added, because the definition provided in the protocol was not specific enough. Escalations were classified into 3 different types: Step-up, step-down or termination. The analysis of the primary endpoint will be conducted overall and per escalation type. A table with all possible treatment type changes has been added together with the corresponding type of escalation.

The assignment of escalations occurring in-between scheduled visits has been mostly aligned with that for the secondary endpoints for consistency across analyses and for greater precision of the assignment. In addition, imputation rules for missing values of covariates to be included in the analyses of the primary endpoint, have been added.

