4 INTERIM AND FINAL ANALYSES

4.1 INTERIM ANALYSIS

A first interim analysis was carried out after 50% of the planned number of patients (i.e. 750 patients) had reached their M12 visit. The M12 interim analysis only considered the secondary endpoints.

Two analysis populations were used:

- 1) M12 Population: all those patients that have completed the M12 visit
- 2) Baseline Population: all those that have completed at least the baseline visit.

A second interim analysis was carried out after 50% of patients had reached their M24 visit. The M24 interim analysis considered the secondary endpoints in addition to summary tables of the primary endpoint (no statistical modelling was undertaken within the interim analysis). Two analysis populations were used:

- 1) M24 Population Set: all those patients that have completed the M24 visit
- 2) M12 Population Set: all those patients that have completed the M12 visit
- 3) Baseline Population Set: all those that have completed at least the baseline visit.

A third Interim Analysis was conducted with a database export of 31st January 2022 following the methods of the second Interim Analysis described above.

The outputs required for the interim analyses were a subset of the final outputs and methods were the same as for the final analysis. Therefore, a separate analysis plan was not required. Details of the output requirements were provided in the list of tables.

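### The SAP's ACR-EULAR Boolean remission rule allows PtGA up to 2 cm where protocol Table 8 allows at most 1 on a 0-10 scale, without explanation, so that rate can only be equal or higher

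*SAP*

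**What the plan says.** Protocol section 6.1.2 (c) lists the remission rate over time on tofacitinib as a secondary endpoint and names the ACR-EULAR Boolean criteria first. Neither that section nor 7.9.2.2.4 gives component limits for those criteria. The limits appear only in section 7.6.7, Table 8: tender joints at most 1, swollen joints at most 1, CRP at most 1 mg/dL, and the patient's global assessment at most "1 on a 0-10 scale".

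SAP section 7.1.2.3 states: "The Rate of Remission will be calculated over time for patients taking tofacitinib, using 5 definitions". For the Boolean one, section 7.1.2.3.1 opens with "ACR Remission is derived as" and then gives the same limits for both joint counts and CRP, but PtGA at most 2 cm. The rate at each visit is the number in remission divided by the number with a non-missing remission status.

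Protocol section 7.6.10 says that PtGA is "recorded using a 100 mm VAS with anchors on 0 = very well and 100 = very poorly". Protocol section 7.9 says: "The SAP may modify the plans outlined in the protocol".

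**The concern.** One named endpoint carries two different limits in two current documents. The SAP limit is the looser, so more patients can qualify as being in remission. No formal comparison is planned (SAP section 9.1.6), so the percentage is itself the result, and the definition determines it.

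The SAP shows elsewhere how it handles a departure from the protocol. For the visit windows, section 2 restates the protocol rule and gives a reason for changing it: "there are likely to be many visits outside of the windows defined in the protocol". Section 2 also covers interim populations, the primary endpoint definition, the assignment of escalations and covariate imputation. It does not mention remission or PtGA, and neither the remission sections (7.1.2.3, 9.2.3.3) nor the summary of analyses (9.2.6) explains the 2 cm limit.

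Interim results are also involved. SAP section 4.1 says of the interim analyses that "methods were the same as for the final analysis", and protocol section 10.1 states: "Results of interim analyses as described in the SAP are planned to be presented on national and international congresses". Boolean remission rates may therefore already have been presented under one limit or the other.

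**Working it through.** The documents state no Boolean remission rate, so there is no figure to reproduce. The check compares the definitions, establishes the direction, and then asks what the size depends on.

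**1. The limits side by side**

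| Component | Protocol Table 8 | SAP 7.1.2.3.1 |
|---|---|---|
| Tender joints (28) | ≤ 1 | ≤ 1 |
| Swollen joints (28) | ≤ 1 | ≤ 1 |
| CRP, mg/dL | ≤ 1 | ≤ 1 |
| PtGA | ≤ 1 on 0-10 = 10 mm | ≤ 2 cm = 20 mm |

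On a 100 mm line, 1 on a 0-10 scale is 10 mm and 2 cm is 20 mm. The other four remission limits (SDAI 3.3, CDAI 2.8, DAS28-4 with ESR and with CRP 2.6) agree between protocol 7.9.2.2.4 and SAP 7.1.2.3, so the departure is isolated.

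**2. Direction**

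Anyone with PtGA at most 10 mm also has PtGA at most 20 mm, so the protocol's remitters are a subset of the SAP's. The SAP does not say how the status is set when one component is missing. Both rules were therefore applied to a grid of 4 × 4 × 4 × 8 = 512 combinations of tender joints, swollen joints, CRP and PtGA, including missing values, under three conventions:

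| Convention | Remission under both | Non-remission → remission | Remission → non-remission | Non-remission → missing |
|---|---|---|---|---|
| Any missing component makes the status missing | 16 | 24 | 0 | 0 |
| A missing component counts as non-remission | 16 | 24 | 0 | 0 |
| One failed component gives non-remission even if others are missing | 16 | 24 | 0 | 57 |

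The 24 are 2 × 2 × 2 passing values of the other components times the 3 grid values of PtGA above 10 and up to 20 mm. The 57 are those same 3 PtGA values times the 3³ − 2³ = 19 patterns in which no other component fails but at least one is missing. These are grid counts, not patient counts.

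Under the first two conventions the numerator can only grow and the denominator is unchanged. Under the third the numerator can only grow and the denominator can only shrink. The rate is equal or higher in every case, and strictly higher whenever a patient with complete data meets the other three limits and has PtGA above 10 and up to 20 mm.

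**3. Size**

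With an unchanged denominator,

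rise in rate = a × b,

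where a is the share of patients meeting the other three limits and b is the share of those with PtGA above 10 and up to 20 mm. The documents give neither. Assuming a = 20-50% and b = 0-30%:

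- lowest: any a × 0% = 0 points
- middle: 35% × 20% = 7 points
- highest: 50% × 30% = 15 points

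**The case against.** The strongest reply is that the SAP is entitled to set this limit. Protocol section 7.9 allows the SAP to modify the plan and reserves amendments for major changes to the primary endpoint. Protocol Table 6 leaves the operational details of PtGA to the SAP. The 2 cm limit is printed openly, and the endpoint is descriptive. All of this stands. A reader might infer a breach of the amendment rule; the documents do not support that.

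SAP section 2 is titled as amendments from previous SAP versions and does not claim to list every departure from the protocol. A limit carried over from an earlier SAP version need not appear there. Silence in that section is therefore weak evidence taken alone. What remains is that the SAP text as a whole does not acknowledge or explain the difference.

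Three further inferences go too far:

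- **That 2 cm is a slip.** The documents do not show whether it is deliberate.
- **That a reader of the study report could not tell which limit was used.** The report is not available, the SAP prints its limit, and the table shells are in a separate document (SAP section 10).
- **That the rate is inflated by a known factor.** The ratio of the two rates is P(PtGA ≤ 20 mm) / P(PtGA ≤ 10 mm) among patients meeting the other three limits. It depends entirely on an assumed distribution. A Beta(0.5, 4.5) shape scaled to 0-100 mm (mean 10 mm) gives 1.27, and a Beta(2, 5) shape (mean 29 mm) gives 3.02. The documents support neither.

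**Conclusion.** The discrepancy is real and should be fixed before the final analysis. The same named criterion has a PtGA limit of 10 mm in the protocol and 20 mm in the SAP, and the SAP does not explain why. The direction is certain and needs no distributional assumption: at each of the eight visits from month 3 to month 24 the Boolean rate is equal to or higher than the protocol-defined rate.

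The size is unknown. The range of 0 to 15 points rests wholly on the assumed shares shown above and is an illustration, not an estimate.

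The reach is limited to one of five remission definitions within secondary endpoint (c), which is summarised descriptively. The SDAI, CDAI and DAS28-4 remission rates, the primary analysis and the sample size are unaffected.

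**What to change.** Before the final analysis, reconcile protocol section 7.6.7 (Table 8) with SAP section 7.1.2.3.1, in one of two ways:

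- apply the Table 8 limit (10 mm) to the endpoint that the protocol names; or
- if 2 cm is intended, say so in the SAP with the reason, give that version its own label, and report the rate under both limits.

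In either case, state the PtGA limit in the table title or footnote. Check which limit the three interim analyses used, and add a note wherever interim and final rates are not comparable.

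The cost is one figure in the SAP and the program, or one extra labelled row in a descriptive table, plus a look back at the interim outputs. No new data are needed, because PtGA and the other components are already on the visit schedule.
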